4. ANALYSIS SETS (POPULATIONS FOR ANALYSIS)

Data for all participants will be assessed to determine if participants meet the criteria for inclusion in each analysis population prior to releasing the database and classifications will be documented per standard operating procedures.

Only participants who signed informed consent will be included in the analysis sets below.

Population	Description
Immunogenicity	All participants who sign the informed consent document: 1) who are household members of interventional study participants (including siblings) who were assigned to foradistrogene movaparvovec or placebo and received a single dose of study treatment and 2) who have at least one day of contact with the interventional study participant during the first 2 weeks.

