5.2. General Methods

For analyses which consider an overall assessment of rates across timepoints, a participant will be considered to have a positive result, if there is at least one positive result after Day 1; similar a participant will be considered to have a negative result if all results after Day 1 are negative.

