5.2.1. Presentation of Continuous and Qualitative Variables

Continuous variables will be summarized using descriptive statistics i.e., number of non-missing values N, mean, median, standard deviation (SD), minimum, maximum and first and third quartile (Q1 and Q3).

Qualitative variables will be summarized by frequency counts and percentages.

In case the analysis refers only to certain visits, percentages will be based on the number of participants with non-missing results at that visit, unless otherwise specified.

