5.3. Methods to Manage Missing Data

Unless otherwise specified, all data will be evaluated as observed, and no imputation method for missing values will be used.

Missing statistics, e.g. when they cannot be calculated, should be presented as 'Not applicable' (NA). For example, if N=1, the measure of variability (SD) cannot be computed and should be presented as 'NA'.

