6. ANALYSES AND SUMMARIES

6.1. Primary Endpoint

6.1.1. Development of NAb to AAV9

- Analysis Set: Immunogenicity ([Section 4](#))
- Analysis methodology: Descriptive statistics ([Section 5.2.1](#)) by visit and overall
- Missing data: Missing data will not be imputed ([Section 5.3](#))

DMB02-GSOP-RF02 5.0 Statistical Analysis Plan Template 05-Dec-2019

PFIZER CONFIDENTIAL

Page 9

TMF Doc ID: 98.03

- Proportions will be provided separately for visits 3 and 4, and overall at any time during the study by the study treatment (fordadistrogene movaparvovec fordadistrogene movaparvovec or placebo) of the interventional study participant. For overall, the response of the participant will be considered as positive if any values in visits 3 and 4 are positive; otherwise the response will be considered as negative.

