6.2. Secondary Endpoint

6.2.1. Development of ADA to AAV9

- Analysis Set: Immunogenicity ([Section 4](#))
- Analysis methodology: Descriptive statistics ([Section 5.2.1](#)) by visit and overall
- Missing data: Missing data will not be imputed ([Section 5.3](#))
- Proportions will be provided separately for visits 3 and 4, and overall at any time during the study by the study treatment (fordadistrogene movaparvovec or placebo) of the interventional study participant. For overall, the response of the participant will be considered as positive if any values in visits 3 and 4 are positive; otherwise the response will be considered as negative.

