Appendix 2. Data Derivation Details

Appendix 2.1. Definition and Use of Visit Windows in Reporting

The below analysis windows will be used.

Safety Parameter	Visit	Target day ¹	Protocol window lower limit	Protocol window upper limit	Analysis window
-Informed consent/assent -Review of incl/excl criteria -Medical history -Demographic information -Weight measurement -Banked biospecimens	1	1			
Extent of contact with the participant in the interventional study	1	1			
	2	Day +14	-0 days	+2 days	
-Concomitant treatments -Adverse event monitoring -Blood Samples for NAb and ADA to AAV9 ² -fordadistrogene movaparvovec vector DNA ²	1	1			
	2	Day +14	-0 days	+2 days	
	3	Day +28	- 8 days	+ 8 days	15 - 42
	4	Day +56	- 10 days	+ 10 days	≥43

¹ Day relative to start of study treatment (Day 1) of the interventional study participant who is in the same household as the study participant.

² If multiple values are in a window the response of the participant will be considered as positive if any values in this window are positive; otherwise the response will be considered as negative.

The following conversion factors will be used to convert days into weeks, months or years:
1 week = 7 days, 1 month = 30.4375 days, 1 year = 365.25 days.

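### Applied as written, the SAP's overall-response rule codes a contact with no Visit 3 and no Visit 4 result as negative, against the no-imputation line in the same sections

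*SAP*

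**What the plan says.** **Overall rule.** For the primary endpoint, SAP 6.1.1 calls the overall response "positive if any values in visits 3 and 4 are positive; otherwise the response will be considered as negative". Sections 6.2.1 and 6.3 close in the same way: "otherwise the response will be considered as negative".

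**Missing data.** Each of these sections also carries the line "Missing data: Missing data will not be imputed" and refers to SAP 5.3, which states: "Unless otherwise specified, all data will be evaluated as observed, and no imputation method for missing values will be used".

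**General rule for overall assessments.** SAP 5.2 words the negative differently: "a participant will be considered to have a negative result if all results after Day 1 are negative".

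**Denominators.** SAP 5.2.1 says: "In case the analysis refers only to certain visits, percentages will be based on the number of participants with non-missing results" at that visit. SAP 5.2.2 defines the denominator per treatment and visit. Neither section defines it for the overall figure.

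**Analysis set.** The Immunogenicity set (SAP 4) takes consented household members of a dosed interventional-study participant "who have at least one day of contact with the interventional study participant during the first 2 weeks". It does not ask for a post-baseline blood sample.

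**The concern.** The word *otherwise* in the overall rule takes in every contact without a positive Visit 3 or 4 value. That includes a contact with no value at either visit. Coding that contact as negative amounts to imputing non-conversion, which the missing-data line beside it rules out.

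Such contacts can arise. Contact days are recorded at Visit 2 (about Day 14, by telephone if need be), so a person can qualify for the set before any post-baseline draw. Protocol 7.1 allows withdrawal at any time, and SAP 2 runs the primary analysis once everyone has either completed or withdrawn.

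The any-time proportion is one of three proportions per treatment group for the primary endpoint, beside Visit 3 and Visit 4. Version 3 of the SAP removed the model-based analysis and the confidence intervals, so these simple proportions are the primary result. The study exists to tell families how large the seroconversion risk is, and the literal rule can err only towards a lower risk. It would also put an overall figure on one denominator rule next to visit figures on another, without saying so.

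**Working it through.** **1. Which contacts are affected**

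| Contact's results at Visits 3 and 4 | SAP 6.1.1 as written | SAP 5.2 | SAP 5.3, as observed |
|---|---|---|---|
| At least one positive | Positive | Positive | Positive |
| One negative, one missing | Negative | Negative | Negative |
| Both negative | Negative | Negative | Negative |
| Both missing | Negative | Not addressed | Missing |

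Only the last row is in dispute.

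**2. Which endpoints are affected**

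The rule reaches NAb seroconversion, ADA seroconversion, boosted NAb and boosted ADA. The vector-DNA endpoint is restricted to participants who seroconvert (SAP 3.3). They already have a post-baseline antibody result, so this group cannot enter that denominator.

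**3. Inputs**

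- Protocol Table 1, 50 enrolled: 33 contacts of treated patients, of whom 33 × 0.75 = 24.75, shown as 25, are NAb seronegative at baseline.
- Protocol Table 1, 250 enrolled: 167 contacts of treated patients, 167 × 0.75 = 125.25, shown as 125.
- As background, the Table 1 interval for n = 25 at 10% reproduces: 10% ± 1.96 × √(0.10 × 0.90 / 25) = 10% ± 11.8%, which is (0, 21.8) after truncation at zero. This point does not dispute it.
- The documents give neither the number of converters nor the number of untested contacts. Both are assumed below. SAP Section 1 cites small enrolment without a figure, so n = 10 is also an assumption.

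**4. Formulas**

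Let x be the converters, n the contacts eligible for the endpoint, k those with neither result, and m = k/n.

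- Literal: x / n
- As observed: x / (n − k)
- Hence literal = as observed × (n − k)/n = as observed × (1 − m)

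**5. Results**

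| n | x | k | Literal | As observed | Gap (points) |
|---|---|---|---|---|---|
| 25 | 2 | 1 | 2/25 = 8.0% | 2/24 = 8.3% | 0.3 |
| 25 | 2 | 2 | 8.0% | 2/23 = 8.7% | 0.7 |
| 25 | 2 | 5 | 8.0% | 2/20 = 10.0% | 2.0 |
| 125 | 10 | 1 | 10/125 = 8.00% | 10/124 = 8.06% | 0.06 |
| 125 | 10 | 5 | 8.00% | 10/120 = 8.33% | 0.33 |
| 10 | 1 | 1 | 1/10 = 10.0% | 1/9 = 11.1% | 1.1 |
| 10 | 1 | 2 | 10.0% | 1/8 = 12.5% | 2.5 |

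Check for n = 25: 8.33% × 0.96 = 8.70% × 0.92 = 10.0% × 0.80 = 8.0%. With k = 0 the two readings coincide. With x = 0 both give 0%.

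**The case against.** The best reply is that the SAP already leans one way. The no-imputation line sits in the same list as the overall rule. Section 5.2 presupposes that results exist. The Appendix 2.1 footnote uses almost the same phrasing in a setting where values must exist: "If multiple values are in a window the response of the participant will be considered as positive" if any of them is. The overall rule must also be read in context for serostatus, since the analysis set does not exclude contacts who are seropositive at baseline; the same courtesy could extend to missing results. On this view *otherwise* covers only contacts with values.

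Much of this stands. An as-observed intent is plausible, and a reader who infers that the sponsor decided to count missing as negative goes further than the text allows. The conflict with 5.3 is also soft, because 5.3 yields to anything specified elsewhere. But that same opening lets a programmer treat the overall rule as the specification. For serostatus the endpoint definition settles the matter; for untested contacts no line settles the overall denominator.

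The objection on size stands too. The group is narrow: it is mainly contacts lost between Visit 2 and Visit 3, the Visit 4 analysis window is open-ended from Day 43, and unacceptable samples may be redrawn. The gaps are small beside the Table 1 interval, and no test or confidence interval in the current SAP uses the figure. Counts shown with percentages would often reveal which denominator was used, though only after the fact.

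Two further inferences are not supported. One is bias between the treatment groups: the factor depends only on m, and the documents give no m for either group. The other is a depressed interim percentage: SAP 7 does not say which rate the external team will report.

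**Conclusion.** The point holds as a minor wording conflict with a possible effect on a primary result. Taken at face value, the overall rule in 6.1.1, 6.2.1 and the two boosted endpoints of 6.3 turns an untested contact into a negative, which the missing-data line of the same sections does not permit. Two competent programmers could report different overall figures from the same data.

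The direction is fixed: the literal figure is never above the as-observed one. The size is modest and rests on assumed counts, at about 0.3 to 2.0 percentage points for 2 converters among 25 with 1 to 5 untested. It is less in a larger sample with similar numbers untested, and somewhat more if very few contacts were enrolled. Visit-specific proportions, contacts with at least one result and the vector-DNA endpoint are unaffected.

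**What to change.** In SAP 6.1 to 6.3, with matching wording in 5.2, define the overall response as follows:

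- positive if any result in the Visit 3 or Visit 4 analysis window is positive;
- negative only if at least one such result exists and all available ones are negative;
- otherwise missing, and excluded from the overall denominator.

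Report the number of contacts with no Visit 3 or 4 result by treatment group.

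The cost is one sentence in each place and one count per group. The downside is a slightly smaller overall denominator. The change brings the overall figure into line with the SAP's own missing-data policy and with the visit figures beside it.

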6.2. Secondary Endpoint

6.2.1. Development of ADA to AAV9

- Analysis Set: Immunogenicity ([Section 4](#))
- Analysis methodology: Descriptive statistics ([Section 5.2.1](#)) by visit and overall
- Missing data: Missing data will not be imputed ([Section 5.3](#))
- Proportions will be provided separately for visits 3 and 4, and overall at any time during the study by the study treatment (fordadistrogene movaparvovec or placebo) of the interventional study participant. For overall, the response of the participant will be considered as positive if any values in visits 3 and 4 are positive; otherwise the response will be considered as negative.

6.3. Exploratory Endpoints

- Boosted NAb to AAV9.
- Boosted ADA to AAV9.
- Detectable fordadistrogene movaparvovec vector DNA.

For each of the endpoints listed above:

- Analysis Set: Immunogenicity ([Section 4](#))
- Analysis methodology: Descriptive statistics ([Section 5.2.1](#)) by visit and overall
- Missing data: Missing data will not be imputed ([Section 5.3](#))
- Proportions will be provided separately for visits 3 and 4, and overall. at any time during the study by the study treatment (fordadistrogene movaparvovec or placebo) of the interventional study participant. For overall, the response of the participant will be considered as positive if any values in visits 3 and 4 are positive; otherwise the response will be considered as negative.

6.4. Subgroup Analyses

Not applicable.

6.5. Baseline and Other Summaries and Analyses

6.5.1. Baseline Summaries

6.5.1.1. Demographic Characteristics

Demographic characteristics and physical measurements will be summarized for all participants and by the interventional study participant's treatment group (fordadistrogene movaparvovec or placebo).

6.5.1.2. Medical History

Medical history will be summarized as the numbers and percentage of participants by MedDRA preferred term (PT) as event category and MedDRA primary system organ class (SOC) as summary category for all participants and by the interventional study participant's treatment group (fordadistrogene movaparvovec or placebo). Each participant will be counted only once within each PT or SOC.

6.5.1.3. Prior Medications

Prior medications will be summarized as the number and percentage of participants by WHO dictionary term for all participants and by the interventional study participant's treatment group (fordadistrogene movaparvovec or placebo).

6.5.2. Study Conduct and Participant Disposition

Participant disposition (e.g., discontinuation from study, reason for discontinuation, completed study, and ongoing) will be summarized by the interventional study participant's treatment group (fordadistrogene movaparvovec or placebo).

6.5.2.1. Extent of Participant Contact

The derived average number of hours per week that the participant is in the same room as the interventional study participants at visit 1 (screening and baseline visit) will be summarized as described in [Section 5.2.1](#).

Number of days of contact in the same room as the interventional study participant during the first two weeks after administration of study treatment will be summarized at visit 2 by the interventional study participant's treatment group (fordadistrogene movaparvovec or placebo) as described in [Section 5.2.1](#).

6.5.3. Study Treatment Exposure

Participants in this study do not receive study treatment and thus, there is no formal exposure analysis planned.

6.5.4. Concomitant Medications

The number and percent of participants who took each concomitant medication will be provided by the interventional study participant's treatment group (fordadistrogene movaparvovec or placebo).

6.6. Safety Summaries and Analyses

6.6.1. Adverse Events

The overall summary of AEs will include the frequency (number and percentage) and severity of AEs by SOC and PT by the interventional study participant's treatment group (fordadistrogene movaparvovec or placebo).

Serious AEs will be listed.

6.6.2. Laboratory Data

Not applicable.

7. INTERIM ANALYSES

To enable potentially informing participants and investigators of the estimated seroconversion rate as soon as possible, an independent, external team of statistician(s) and programmer(s) will be established to estimate the seroconversion rates. Only summary seroconversion rates will be communicated. In order to minimize possibility of unblinding internal study team, the external vendor will provide only the percent of participants whose family members received fordadistrogene movaparvovec and converted.

9. APPENDICES

Appendix 1. Summary of Efficacy Analyses

Not applicable.

Appendix 2. Data Derivation Details

Appendix 2.1. Definition and Use of Visit Windows in Reporting

The below analysis windows will be used.

Safety Parameter	Visit	Target day ¹	Protocol window lower limit	Protocol window upper limit	Analysis window
-Informed consent/assent -Review of incl/excl criteria -Medical history -Demographic information -Weight measurement -Banked biospecimens	1	1			
Extent of contact with the participant in the interventional study	1	1			
	2	Day +14	-0 days	+2 days	
-Concomitant treatments -Adverse event monitoring -Blood Samples for NAb and ADA to AAV9 ² -fordadistrogene movaparvovec vector DNA ²	1	1			
	2	Day +14	-0 days	+2 days	
	3	Day +28	- 8 days	+ 8 days	15 - 42
	4	Day +56	- 10 days	+ 10 days	≥43

¹ Day relative to start of study treatment (Day 1) of the interventional study participant who is in the same household as the study participant.

² If multiple values are in a window the response of the participant will be considered as positive if any values in this window are positive; otherwise the response will be considered as negative.

The following conversion factors will be used to convert days into weeks, months or years:
1 week = 7 days, 1 month = 30.4375 days, 1 year = 365.25 days.

Appendix 2.2. Endpoint Derivations

For the extent of contact with the participant in the interventional study, the CRF uses a drop-down selection at baseline (see the table below) that will be converted into a continuous variable as follows:

Table: Numeric transformation for derived average hours of contact per week

Average number of hours of contact per week as collected in CRF at visit 1	Derived average number of hours of contact per week
--	---

10 - 12	11
13 - 16	14.5
17 - 20	18.5
21 - 24	22.5
25 - 30	27.5
31 - 36	33.5
37 - 42	39.5
43 - 48	45.5
49 - 60	54.5
61 - 72	66.5
73 - 84	78.5
85 - 96	90.5
97 - 120	108.5
121 - 144	132.5
145 - 168	156.5

Appendix 2.3. Definition of Protocol Deviations that Relate to Statistical Analyses/Populations

Not applicable.

Appendix 3. Data Set Descriptions

None.

Appendix 4. Statistical Methodology Details

None.

Appendix 5. SAP Amendment History

The summary of changes for the current SAP amendment are described in Section **Error! Reference source not found.**. The summary of changes for past amendments can be found below.

Version/ Date	Associated Protocol Amendment	Rationale	Specific Changes
19 May 2020			Original SAP
V2/20Apr2022	protocol amendment #1	Updates following protocol amendment	
 Global updates: Changed 'C3391003' to the 'interventional study' (which may include study C3391003, C3391002, C3391008, or C3391001)

		
 Changed PF-06939926 to fordadistrogene movaparvovec
		
Protocol title Modified 'substudy' to 'study'

		
Section 2.1 Removed 'and have a household contact being treated with PF-06939926 or placebo in Study C3391003' from study objectives

	SAP content clarification	
Section 4 and 6 Removed 'Enrolled population' Modified 'Safety' population to 'Immunogenicity'

		
Section 5.2 Modified wordings for overall assessment

		
Section 5.2.2.1 Added the statistical method for calculating observed proportions (95% CIs) and the difference in observed proportions (95% CI)

		
Section 5.2.2.2 Clarified the approach for handling GEE model convergence issues

		
Section 6 Added descriptive statistics in addition to GEE model estimates for primary, secondary and exploratory endpoints

		
Section 6.1 and 6.2 Added descriptive statistics in the analysis methodology for the primary and secondary endpoints

		
Section 6.5.4 Removed 'according to Pfizer data standards'

		
Section 7 Added texts to clarify the interim analysis

		
Appendix 2.2 Modified the column names of the table

Appendix 6. List of Abbreviations

Abbreviation	Term
AAV9	adeno associated virus serotype 9
ADA	anti-drug antibody
AE	adverse event
BMI	body mass index
CI	confidence interval
CRF	case report form
DMD	Duchenne muscular dystrophy
DNA	deoxyribonucleic acid
GEE	generalized estimating equation
MedDRA	medical dictionary for regulatory activities
NA	not applicable
NAb	neutralizing antibody
NE	non-estimable
PT	preferred term
Q1	first quartile
Q3	third quartile
SAP	statistical analysis plan
SD	standard deviation
SE	standard error
SOC	system organ class
WHO	World Health Organization
